5.1.1 Risks Associated with Pirfenidone

Treatment with pirfenidone was consistent with the known safety profile and generally well tolerated in patients who received treatment in the clinical development program.

Almost all patients experienced an adverse event (99.0% in the pirfenidone 2403 mg/day group and 97.9% in the placebo group). The most common adverse events in the pirfenidone group were GI events (nausea, diarrhea, dyspepsia, vomiting, gastroesophageal reflux disease [GERD], and constipation), respiratory-related events (cough, dyspnea, IPF, upper respiratory tract infection, nasopharyngitis, bronchitis, and sinusitis), fatigue, decreased weight, anorexia, back pain, arthralgia, headache, dizziness, insomnia, rash, and photosensitivity reactions.

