5.3.5.7 Deaths

For this protocol, mortality from any cause and mortality from respiratory diseases are included as efficacy endpoints. Mortality is also included as part of the PFS efficacy endpoint. Deaths that occur during the protocol-specified adverse event reporting period (see Section 5.3.1) that are attributed by the investigator solely to progression of unclassifiable ILD should be recorded on the Death Attributed to Progressive Disease eCRF. All other on-trial deaths, regardless of relationship to trial treatment, must be recorded on the Adverse Event eCRF and immediately reported to the Sponsor (see Section 5.4.2). The iDMC will monitor the frequency of deaths in this trial.

Death should be considered an outcome and not a distinct event. The event or condition that caused or contributed to the fatal outcome should be recorded as the single medical concept on the Adverse Event eCRF. Generally, only one such event should be reported.

The term "**sudden death**" should be used only for the occurrence of an abrupt and unexpected death due to presumed cardiac causes in a patient with or without pre-existing heart disease, within 1 hour after the onset of acute symptoms or, in the case of an unwitnessed death, within 24 hours after the patient was last seen alive and stable. If the cause of death is unknown and cannot be ascertained at the time of reporting, "**unexplained death**" should be recorded on the Adverse Event eCRF. If the cause of death later becomes available (e.g., after autopsy), "unexplained death" should be replaced by the established cause of death.

Deaths that occur after the adverse event reporting period should be reported as described in Section 5.6.

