5.3.5.9 Lack of Efficacy or Worsening of Unclassifiable ILD

Events that are clearly consistent with the expected pattern of progression of the underlying disease should not be recorded as adverse events. These data will be captured as efficacy assessment data only. In most cases, the expected pattern of progression will be based on $\geq 10\%$ relative decline in FVC or a >50 m decline in 6MWD. In rare cases, the determination of clinical progression will be based on symptomatic deterioration or a decline in DLco of $\geq 15\%$. However, every effort should be made to document progression through use of objective criteria. If there is any uncertainty as to whether an event is due to disease progression, it should be reported as an adverse event.

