5.3.5.10 Hospitalization or Prolonged Hospitalization

Any adverse event that results in hospitalization (i.e., inpatient admission to a hospital) or prolonged hospitalization should be documented and reported as a serious adverse event (per the definition of serious adverse event in Section 5.2.2), except as outlined below.

The following hospitalization scenarios are not considered to be adverse events:

- Hospitalization for respite care

- Hospitalization for a pre-existing condition, provided that all of the following criteria are met:
 - The hospitalization was planned prior to the trial or was scheduled during the trial when elective surgery became necessary because of the expected normal progression of the disease
 - The patient has not experienced an adverse event
- Hospitalization due solely to progression of the underlying ILD

The following hospitalization scenarios are not considered to be serious adverse events, but should be reported as adverse events instead:

- Hospitalization that was necessary because of patient requirement for outpatient care outside of normal outpatient clinic operating hours.

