TEAEs and SAEs from day 1 of dosing until 168 days for MA39189 will be compared with the data from the registrational phase III studies in IPF patients CAPACITY1 and 2 and ASCEND (restricted to first 168 days after first dose). The following parameters will be displayed in this analysis:

- duration of study in patient years (PY), calculated as sum of all patient's observation times).
- number of patients with at least one event,
- number of all events, defined as all AEs from all patients with onset date during observation time period
- rate of events per 100 PYs observation time, calculated as [number of events/duration] * 100
- 95% CI for this rate with
 - o Lower limit = $100*[number of events z_{1-\alpha/2}* SQRT(number of events)]/duration$
 - o Upper limit = 100*[number of events + $z_{1-\alpha/2}$ * SQRT(number of events)]/duration

where $z_{1-\alpha/2}$ is the 1- $\alpha/2$ quantile of the standard normal distribution.

Patients who withdrew from treatment during first 168 days of dosing will be censored at day of withdrawal for this analysis. The analysis will be repeated for all TEAEs/SAEs from first day of dosing until 28 days of last dose, irrespective of the different study durations for MA39189 versus the phase III studies.

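### The SAP's adverse event rate table against the phase III IPF studies aligns follow-up time but not what counts as an event, which tilts the comparison toward lower rates in MA39189

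*SAP*

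**What the plan says.** **The comparison.** SAP 4.6.2 (Adverse Events, table of rates per 100 patient-years) takes "TEAEs and SAEs from day 1 of dosing until 168 days for MA39189" and says that these "will be compared with the data from the registrational phase III studies in IPF patients CAPACITY1 and 2 and ASCEND", with the phase III data cut to the first 168 days after first dose. The numerator is the "number of all events, defined as all AEs from all patients with onset date during observation time period". The rate is the "rate of events per 100 PYs observation time, calculated as [number of events/duration] * 100". Patients who withdraw from treatment are censored at withdrawal. The SAP gives no rule for excluding or aligning events that represent worsening of the lung disease. The repeat of the analysis up to 28 days after last dose has the same numerator.

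**What MA39189 records.** Three protocol rules keep disease progression out of the adverse event data:
- Section 5.3.5.9: "Events that are clearly consistent with the expected pattern of progression of the underlying disease should not be recorded as adverse events". Such events are kept as efficacy data only. Where there is doubt, the event is still to be reported as an adverse event.
- Section 5.3.5.10: "Hospitalization due solely to progression of the underlying ILD" is on the list of scenarios that are not adverse events, so it cannot be an SAE.
- Section 5.3.5.7: deaths in the reporting period that the investigator attributes to progression alone "should be recorded on the Death Attributed to Progressive Disease eCRF". All other on-trial deaths go on the Adverse Event eCRF.

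**What the earlier data contain.** Protocol 5.1.1 lists, among the most common adverse events on pirfenidone, "respiratory-related events (cough, dyspnea, IPF, upper respiratory tract infection, nasopharyngitis, bronchitis, and sinusitis".

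**The concern.** A rate comparison across studies is interpretable only if the same clinical course produces the same count in each. The SAP takes care over follow-up time, with its 168-day cut and censoring rule, but not over the event definition. A patient whose disease clearly progresses adds nothing to the MA39189 numerator. In the earlier IPF data, at least some worsening of the underlying disease appears to have been counted.

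The table is one of two added for regulatory purposes. A reader who sees a lower SAE rate in unclassifiable ILD than in IPF would probably credit the drug or the population. Nothing planned for the table says that part of the difference could come from how events were recorded.

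**Working it through.** The plan states no adverse event rate, so there is no figure to reproduce for the claim itself. The only planning figure used below, 125 per arm, does reproduce: a t-test with a 25 mL difference (85 − 60) and SD 70 mL has 80.3% power at 125 per arm.

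**Step 1. Recording rules side by side**
- *Clear progression:* not an adverse event in MA39189 (5.3.5.9). In the earlier data, IPF is a listed common adverse event (5.1.1). In patients who all have IPF at entry, that term most naturally means worsening of the disease.
- *Admission due solely to progression:* not an adverse event in MA39189 (5.3.5.10). The phase III rule is not given.
- *Death attributed solely to progression:* separate form in MA39189 (5.3.5.7). The phase III rule is not given.
- *Doubtful or mixed cases:* recorded as adverse events in MA39189.

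For an identical clear progression event, the count can therefore be 1 in the comparator and 0 here. The reverse cannot arise from these rules, so the direction is downward for MA39189.

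**Step 2. Is the 5.1.1 list the phase III data?** Protocol 5.1.1 refers to the clinical development program, not to phase III. The link is an inference:
- It contrasts 2403 mg/day with placebo.
- Its subsections 5.1.1.5 to 5.1.1.7 cite a pooled phase 3 analysis (PIPF-004/006/016).
- The counts there imply one common denominator: 112/0.180 = 622, 162/0.260 = 623 and 63/0.101 = 624, so about 623 pirfenidone patients.
- Protocol 1.2 identifies Studies 004 and 006 as the CAPACITY trials. Neither document states that 016 is ASCEND.

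**Step 3. Scale of one missing event.** Using the SAP formula for one arm of 125 patients followed 168 days with no withdrawals:
- Patient-years = 125 × 168 / 365.25 = 57.5
- One unrecorded event = 100 / 57.5 = 1.74 per 100 patient-years

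**Step 4. Illustration (all inputs below are assumptions).** Let a share *x* of patients have one progression event that is not recorded. The fall in the rate is 100 × 125*x* / 57.5:
- *x* = 2%: 2.5 events, 4.3 per 100 patient-years
- *x* = 5%: 6.25 events, 10.9 per 100 patient-years
- *x* = 10%: 12.5 events, 21.7 per 100 patient-years

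Relative to an assumed rate with these events counted:
- All TEAEs at 600–1200 per 100 patient-years: from 4.3/1200 = 0.4% to 21.7/600 = 3.6%
- SAEs at 30–70 per 100 patient-years, if every such event were serious: from 4.3/70 = 6% to 21.7/30 = about 73%

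The 73% is an extreme corner: 12.5 of about 17 SAEs would have to be sole, clear progression.

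**Step 5. Against sampling error.** The SAP interval has half-width 100 × 1.96 × √events / patient-years. For all TEAEs at 600–1200 this is 63.3–89.5, well above the shift. For SAEs at 30–70 it is 14.2–21.6, the same order as the shift.

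**The case against.** The strongest case against is that the comparator half is thin. Neither document gives the recording rules of CAPACITY or ASCEND. The evidence is one term in a list that is not itself labelled phase III. A study run under MA39189's own rule would also collect some disease-worsening events, because doubtful cases are recorded. This stands, and it limits the conclusion to a direction.

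The exclusions are also narrow. Section 5.3.5.9 bases the expected pattern mostly on FVC or walk-distance decline, which is test decline more than serious illness. The admission and death exclusions apply only when progression is the sole cause. SAP 4.5.8 describes deaths and other intercurrent events as few. These points also stand, and they argue against assuming a large effect.

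The events are not lost to the report. SAP 4.6.3 tabulates deaths by arm, and SAP 4.5.3 analyses all-cause and respiratory non-elective hospitalization and time to death. That is true, but none of these puts the events back into the rate table or tells its reader that they are absent.

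Two stronger readings are tempting and are not supported. A reader might infer that MA39189 rates must come out lower by construction. They need not: only clear progression is excluded, and the populations differ. A reader might also take the share of phase III SAEs coded as disease worsening as the understatement here. That treats every such event as clear, sole progression that MA39189 would have left out. It is at most an upper bound, and the documents do not give the share.

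**Conclusion.** The point holds as a directional bias in an external comparison. Followed as written, the table compares rates built on event definitions that appear to differ, and all else equal the MA39189 rate is biased downward relative to phase III. This rests on two inferences: that the 5.1.1 list reflects the phase III pool, and that the IPF term there means worsening of the underlying disease. If the sponsor knows that the phase III rules matched, one sentence saying so disposes of the point.

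The size cannot be derived from the documents. Under the assumed ranges it is probably small for all TEAEs and may be material for SAEs. The TEAE line for patients with at least one event is probably little affected, since 99.0% on pirfenidone and 97.9% on placebo had an event in the earlier data.

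The randomized pirfenidone–placebo safety comparison is not affected, because both arms follow the same recording rule. No primary or secondary efficacy result changes. This is a cheap improvement to a supplementary table.

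**What to change.** In SAP 4.6.2, for the table of rates per 100 patient-years and its repeat to 28 days after last dose:

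1. Keep the all-event TEAE and SAE rates as planned.
2. Add a parallel row for TEAEs and for SAEs that excludes, from both sources, a list of disease-worsening preferred terms (IPF, ILD, pulmonary fibrosis and similar), fixed before the table is run.
3. Footnote the MA39189 recording rules from Protocol 5.3.5.7, 5.3.5.9 and 5.3.5.10 and, if known, those of the phase III studies.
4. Show the number of MA39189 deaths from the Death Attributed to Progressive Disease eCRF next to the SAE rate.

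The filter should work on preferred terms only. Removing phase III admissions or deaths due solely to progression would need attribution data that the documents do not show to exist.

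The cost is a term list, a footnote and a little extra programming. There are three downsides. The filtered phase III figures will differ from those published earlier. The filtered row also drops the doubtful worsening events that MA39189 did record. And the list is set after the March 2019 primary analysis, so the row should be labelled supplementary.

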5.3.5.3 Persistent or Recurrent Adverse Events

A persistent adverse event is one that extends continuously, without resolution, between patient evaluation time points. Such events should only be recorded once on the Adverse Event eCRF. The initial severity (intensity or grade) of the event will be recorded at the time the event is first reported. If a persistent adverse event becomes more severe, the most extreme severity should also be recorded on the Adverse Event eCRF. If the event becomes serious, it should be reported to the Sponsor immediately (i.e., no more than 24 hours after learning that the event became serious; see Section 5.4.2 for reporting instructions). The Adverse Event eCRF should be updated by

changing the event from "non-serious" to "serious," providing the date that the event became serious, and completing all data fields related to serious adverse events.

A recurrent adverse event is one that resolves between patient evaluation time points and subsequently recurs. Each recurrence of an adverse event should be recorded as a separate event on the Adverse Event eCRF.

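### The 95% interval for adverse-event rates per 100 patient-years treats repeat events as independent, so it is too narrow when rates vary between patients; in any low-count row it also breaks down

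*SAP*

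**What the plan says.** SAP version 3.0, section 4.6.2, adds two tables for regulatory use. The second compares adverse-event rates per 100 patient-years in this trial with the registrational phase III studies in IPF. It covers "TEAEs and SAEs from day 1 of dosing until 168 days for MA39189", with the phase III data cut to the same length, and is then repeated for the period up to 28 days after the last dose.

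The ingredients are:

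- Rate: "rate of events per 100 PYs observation time, calculated as [number of events/duration] * 100".
- Numerator: "number of all events, defined as all AEs from all patients with onset date during observation time period".
- Denominator: "duration of study in patient years (PY), calculated as sum of all patient's observation times".
- Interval: a "95% CI for this rate with" symmetric limits. The upper limit starts "Upper limit = 100*[number of events" and adds z times the square root of the event count, all divided by duration. The lower limit is read as its mirror image. Here z is the 1 − α/2 "quantile of the standard normal distribution".

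Protocol section 5.3.5.3 settles how repeats enter the numerator: "Each recurrence of an adverse event should be recorded as a separate event on the Adverse Event eCRF".

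The table also displays the number of patients with at least one event. Neither document gives a rule for zero events, a bound at zero, an exact or log-scale method, a minimum count, or an allowance for several events from one patient.

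**The concern.** The square root of the event count is the right standard error only if events arrive independently at one common rate. Here one patient can contribute many events, and patients usually differ in how readily they report or develop them. The count then varies more than a Poisson count with the same mean, and the stated interval is too short. This bears most on total treatment-emergent events, where repeats are most common.

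A second weakness is that the normal approximation is poor when the count is small.

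What is at stake is how precise a comparison across studies looks. SAP section 4.6 rules out formal tests of safety, so the interval is the only measure of uncertainty attached to these rates. Intervals that are too short on both sides can make a chance difference between this trial and the phase III studies look real.

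**Working it through.** The SAP prints a formula and no numerical rate or interval, so there is no figure to reproduce. The formula was evaluated directly.

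**Inputs from the documents**

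- z = 1.960, so z² = 3.84 (SAP 4.6.2).
- Window 168 days (SAP 4.6.2); 365.25 days per year (SAP 4.2).
- 125 patients per arm (Protocol 6.1, SAP 2.3), used only for scale. Maximum exposure per arm, with no withdrawals: 125 × 168 / 365.25 = 57.5 patient-years.

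**Inputs not in the documents (assumed)**

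- m, mean events per patient: 0.2, 1, 4.
- k, variance between patients of a rate multiplier with mean 1: 0, 0.25, 0.5, 1.

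**Step 1: repeat events.** If patient i has a Poisson count with mean λᵢ, and the λᵢ have mean m and variance km², then Var(count) = m + km² = m(1 + km). For N patients the total has variance Nm(1 + km). The SAP uses the total itself, about Nm. The correct width is therefore √(1 + km) times the SAP width, and 1 + km is the variance/mean ratio.

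Coverage of the SAP interval, from gamma-Poisson simulation (125 patients with equal follow-up, 20,000 runs); width factor in brackets:

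| m | k = 0 | k = 0.25 | k = 0.5 | k = 1 |
|---|---|---|---|---|
| 0.2 | 95% (1.00) | 94% (1.02) | 93% (1.05) | 92% (1.10) |
| 1 | 95% (1.00) | 92% (1.12) | 89% (1.22) | 83% (1.41) |
| 4 | 95% (1.00) | 83% (1.41) | 74% (1.73) | 61% (2.24) |

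The approximation 2Φ(1.96/√(1 + km)) − 1 agrees: ratios of 2, 3 and 5 give 83%, 74% and 62%. An interval using the observed between-patient variance covered 93.8% to 94.9% across the simulated settings.

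For scale, take m = 4, so 125 × 4 = 500 events. The rate is 100 × 500 / 57.495 = 869.6, and the SAP half-width is 100 × 1.96 × √500 / 57.495 = 76.2, giving 793 to 946. With k = 0.5 the half-width should be 76.2 × 1.73 = 132, giving about 738 to 1,002.

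**Step 2: small counts.** The lower limit is negative when n < z√n, that is when 0 < n < 3.84: at 1, 2 or 3 events, whatever the duration. At n = 0 both limits are zero. Per 100 patient-years at 57.5 patient-years:

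| Events | SAP limits | Exact Poisson limits |
|---|---|---|
| 0 | 0.00 to 0.00 | 0.00 to 6.42 |
| 1 | −1.67 to 5.15 | 0.04 to 9.69 |
| 2 | −1.34 to 8.30 | 0.42 to 12.57 |
| 3 | −0.69 to 11.12 | 1.08 to 15.25 |
| 4 | 0.14 to 13.78 | 1.90 to 17.81 |

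With purely Poisson counts, coverage of the SAP interval is 63%, 80% and 87% at expected counts of 1, 3 and 5, then 93% at 10 and 95% at 20. At an expected count of 1, nearly all the loss comes from the zero count: its probability is 0.368, and 1 − 0.368 = 0.632.

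**The case against.** The case on the other side has four parts.

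- **Layout.** The rate table names only treatment-emergent and serious events. The companion table in the same section is explicitly split by system organ class; this one is not. Protocol 5.1.1 reports that 99.0% of pirfenidone and 97.9% of placebo patients in the earlier programme had an adverse event. Follow-up there was partly longer, so this is only a guide, but an overall total should be far above three events. This stands: small-count failure is conditional on sparse rows being shown.
- **Size.** No document gives events per patient or the variation between patients. At 0.2 events per patient, which could suit serious events, coverage falls only to 92–94%. This stands too: direction is established, size is not.
- **Consequence.** The table is descriptive, and no decision rule uses it. This stands, and limits how serious the point is.
- **Visibility.** The table shows patients with an event beside the number of events, and patient-level incidence is tabulated elsewhere in section 4.6.2. This helps a reader notice repeats but does not correct the interval.

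A reader might infer that the table will contain negative or empty intervals, or that its intervals really cover only 61% to 83%. The documents support neither. The first needs a layout the SAP does not specify; the second needs values of m and k it does not supply.

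**Conclusion.** The interval is wrong as written for the quantity it accompanies. It uses Poisson variance on a count that includes repeats, and is too narrow by √(1 + km) whenever rates differ between patients. Total treatment-emergent events are the main case. For rare serious events the loss may be slight, and with no between-patient variation there is none.

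The failure at 0 to 3 events is certain algebra, but it matters only if low-count rows appear. Under Poisson counts it has gone by about 20 events.

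The conclusion rests on the SAP formula, the rule that recurrences count separately, and the assumed range for m and k. It would be wrong to infer that the rate itself is faulty or that the safety or efficacy conclusions of the trial are undermined: the point estimate is sound, and the effect is confined to the apparent precision of a supplementary comparison. It should be corrected because correction is cheap.

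**What to change.** Keep the rate as defined and replace the two limit lines in SAP 4.6.2:

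- Fit a Poisson model to each patient's event count with log follow-up as offset. Take patient-clustered (robust) standard errors on the log scale and back-transform the limits, which then cannot be negative.
- Use exact Poisson limits where counts are too small for that model, including zero events, and state the switching count in advance. Exact limits still assume independent events, so read them beside the number of patients with an event.
- Apply the same method to the phase III data, so that both sides of the comparison carry comparable intervals.
- State whether the table is split by system organ class or preferred term, since that decides whether sparse rows arise.

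A separate first-event rate is not needed: it would be a new quantity with a different denominator. A negative binomial or robust model alone would not suffice either, because it gives no limits at zero events.

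The cost is a few lines of SAP text and code, with no new data collection. Intervals for total events become wider: √2 = 1.4 to √5 = 2.2 times at variance/mean ratios of 2 to 5. Apparent differences between studies may look less certain as a result.
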